# Monitoring of safety:

Although it is potentially beneficial and has been safely performed in ICU patients, there are only limited data about FBT safety in patients with potentially disrupted intestinal barrier. In turn, following measures have been taken to maximise safety of the current study for patients:

- Treating clinician will not be blinded to treatment allocation and they will be encouraged to speak up should any safety concerns arise.
- Before and 3 hours after FMT, vital signs, blood cultures, endotoxin and early cytokine levels will be measures to specifically look at potential bacterial translocation.
- All patients' vital functions will be continually monitored as per local standards. Frequency, volume and character (as per Bristol scale) of stools will be recorded in 12 hour intervals.
- Onset of sepsis or elevation lactate > 2mM or the presence of pyrexia >38 C with >30% rise of inflammatory markers without clear alternative reason (e.g. HAP) will trigger, in both groups, the addition of intravenous tigecycline or intravenous vancomycine, if C. dif positivity is known or suspected.
- I.v. antibiotics efficient against C. dif. can be added in both groups if a treating clinician considers this appropriate. Reason for doing so will be recorded.
- Should a SUSAR appear, it will be reported as per local legislature and within 48 hours reviewed by the team of investigators, together with independent safety advisors (prof. [name]. Dept. of Infectious Diseases, Na Bulovce Hospital, Prague and Dr.[name], REB Chair FNKV Univ. Hospital), a representative of nursing staff independent on the study. Two SUSARs in the intervention group would automatically lead to termination of the trial for safety reasons.

Unique Protocol ID: 2021-002290-25 22.9.2021 Protocol version 9.2

In addition, the same team will meet ad hoc whenever safety concerns arise. The
team will review data collected from first 8 subjects who have been randomised and
focus on the analysis of adverse events. In particular, the team will review the dynamics of body temperature, heart rate, blood pressure, lactate and blood cultures
before and after FMT. The decision will be taken to continue or terminate the study.

# Statistical plan:

Safety parameters will be reported on intention-to-treat basis. Primary outcome will be compared by as unadjusted hazard ratio of not being cured (with 95% interval) in a per protocol analysis. The subset of patients with C. dif positivity will be analysed separately.

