## Abstract:

*Background:* Postantibiotic diarrhoea in critically ill patients is common, often protracted and currently there is no effective treatment of it.

*Aim*: To test safety and feasibility of faecal microbial transplantation in critically ill patients with postantibiotic diarhoea.

Design: Prospective, single center, parallel group randomised controlled trial. Subjects: ICU patients (both general and burn ICU) who developed diarhea after a curse of antibiotic therapy that is persistent for 24 hours even after interruption of enteral nutrition. Patients with septic shock or approaching death will be excluded.

Treatment in the intervention group: Faecal bacteriotherapy (FBT) delivered as enema (and repeated once in the subgroup of patients with C. dif. infection) of 350 ml of standardised mixed transplantate prepared from faeces of 7 healthy donors. Control group: Standard-of-care protocolised treatment of postantibiotic diarhea (which includes vancomycine 250 mg p.o. 6 hourly in the subgroup with C. dif. infection).

22.9.2021 Protocol version 9.2

*Primary outcome*: Percentage of patients with treatment failure at day 7 after randomisation, which is defined as treatment either not being delivered or effective. *Secondary and exploratory outcomes*: Influence of the intervention on colonic microbiom and metabolom, small bowel and colonic permeability, bacterial translocation and systemic inflammation.

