# Primary end-point:

• Percentage of patients with treatment failure at day 7 after randomisation. Treatment failure is defined as either failure to administer allocated treatment for any reason or the presence of diarrhoea on day 7 after randomisation (as assessed by personnel blinded to treatment allocation).

22.9.2021 Protocol version 9.2

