#### Sample study size:

We plan to randomise 36 patients in 1:1 ratio: This is a pilot trial, with primary outcome being feasibility and safety of faecal bacterial transplantation in the population of critically ill adults with C. dif. positivity and diarrhoea. However, with 36 randomised patients, the study will have sufficient power to determine non-inferiority against standard-of-care based on data available in FBT in patients with C. dif. In two trials in non-critically ill patients, the success of FBT was 69% (22 out of 32) or 56% (5 out of 9) as compared to 45% cured by oral metronidazole. Assuming that clinically significant difference between the two methods is 20% and the intervention will be as effective in ICU patients as it was in the non-critically ill group (curing 27 out of 41, ie. 66%), if there is a true difference in favour of the experimental treatment of 21%, then 36 patients are required to be 80% sure that the upper limit of a one-sided 95% confidence interval (or equivalently a 90% two-sided confidence interval) will exclude a difference in favour of the standard group of more than 20%. The expected duration of participation in the study is 6 months.

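### Safety is reported by allocation only, so events that can occur only after faecal bacteriotherapy (FBT) get a denominator that may include patients never given it

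*Combined protocol and SAP*

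**What the plan says.** The Statistical plan section is very short. Its only sentence on safety is "Safety parameters will be reported on intention-to-treat basis". No section defines a safety population, an as-treated analysis or a denominator of patients actually given FBT. No confidence limit and no test for safety is planned.

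Four other parts of the document bear on this.

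- **Safety is a main aim.** The Abstract gives the aim as "To test safety and feasibility of faecal microbial transplantation in critically ill patients", and the sample size section describes a pilot "with primary outcome being feasibility and safety of faecal bacterial transplantation". In the list of endpoints, however, adverse events are secondary.
- **Non-delivery is foreseen.** The Primary end-point section counts "failure to administer allocated treatment for any reason" as treatment failure. It gives no rate.
- **Some safety items require exposure.** The composite under Secondary end-points combines general events (new-onset sepsis, toxic megacolon) with a positive blood culture after FBT and other serious adverse events judged possibly related to FBT.
- **Safety data are collected around the procedure.** The Intervention group and Monitoring of safety sections schedule vital signs and blood cultures around FBT. The section on source data requires the FBT procedure to be documented for each patient.

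**The concern.** A patient allocated to FBT who never receives it cannot have a blood culture after FBT or an adverse reaction to it. Under the stated rule that patient still counts in the FBT arm's denominator. For these events the reported proportion then answers a question about being allocated to FBT, while the trial's aim asks what happens to critically ill patients who are given it.

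The Monitoring of safety section itself acknowledges that data are limited in patients whose intestinal barrier may be disrupted. With about 18 patients in the arm, the most likely form of a safety conclusion is a small count with an upper limit, and that limit depends directly on the denominator. If the plan does not fix a dosed denominator, it will be chosen after the results are known, or the allocated number will be used by default.

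**Working it through.** **Inputs.** "We plan to randomise 36 patients in 1:1 ratio", so 36 / 2 = 18 patients are allocated to FBT. The number dosed, m, is not given. I take m = 17, 16 and 14 as assumptions and m = 18 as full delivery.

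**Step 1: reproduce the plan's sample size.** The control cure rate is 0.45 ("as compared to 45% cured by oral metronidazole") and the FBT cure rate is 0.66 ("curing 27 out of 41, ie. 66"%). The margin is 0.20, one-sided alpha 5% and power 80%. With unpooled variance:

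n per arm = (1.645 + 0.842)² × (0.45 × 0.55 + 0.66 × 0.34) / (0.21 + 0.20)² = 6.18 × 0.4719 / 0.1681 = 17.4, rounded up to 18.

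The total is 36, as stated, so 18 is the correct allocated denominator.

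**Step 2: dilution of FBT-specific events.** If such an event has rate p in dosed patients and cannot occur in the others, the expected intention-to-treat rate is p × m/18. The table takes p = 20% as an illustration.

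**Step 3: upper limit with no events.** The exact limit is 1 − a^(1/m), with a = 0.05 for a one-sided 95% limit and a = 0.025 for the upper end of a two-sided 95% interval.

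| Dosed, m | Delivered share m/18 | Intention-to-treat rate if p = 20% | One-sided 95% limit | Two-sided 95% upper limit |
|---|---|---|---|---|
| 18 | 1.00 | 20.0% | 15.3% | 18.5% |
| 17 | 0.94 | 18.9% | 16.2% | 19.5% |
| 16 | 0.89 | 17.8% | 17.1% | 20.6% |
| 14 | 0.78 | 15.6% | 19.3% | 23.2% |

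An analysis on the allocated number uses the first row's limits whatever m turns out to be. On the one-sided limit, the understatement is 0.9 points with one undosed patient, 1.8 with two and 4.0 with four.

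**Step 4: general events.** For an event such as sepsis, undosed patients have their own rate q, and the expected intention-to-treat rate is [m × p + (18 − m) × q] / 18. Take p = 30% as an illustration.

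- If q = 10%: m = 16 gives (4.8 + 0.2)/18 = 27.8%, and m = 14 gives (4.2 + 0.4)/18 = 25.6%. Both are below 30%.
- If q = 50%, because undosed patients are sicker: m = 16 gives (4.8 + 1.0)/18 = 32.2%, and m = 14 gives (4.2 + 2.0)/18 = 34.4%. Both are above 30%.

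The sign of the bias therefore depends on q, about which the documents say nothing.

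**The case against.** **Non-delivery may be rare.** The eligibility criteria exclude patients who cannot tolerate an enema, who are near death, or for whom the clinician judges FBT unsafe or not feasible. Randomisation is on the evening of day 0 and FBT follows on day 1, which leaves little time for plans to change. This stands as a limit on size: with full delivery the two denominators coincide, and with one undosed patient the limit moves by less than a point. A reader might infer that substantial non-delivery is expected, but the documents only provide for the possibility.

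**FBT-specific harms are already tied to exposure.** They are defined by the procedure, measured around it, and counted the same way under either analysis. The number dosed will also be known, because non-delivery is part of the primary endpoint. This stands too, and it keeps the consequence modest. But the monitoring arrangements do not set the denominator for the final report, and the Statistical plan names only the allocated one.

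**Intention-to-treat preserves the randomised comparison.** It does, and it should stay. A by-exposure set could drop the sickest patients of the FBT arm and so make FBT look safer than it is. For that reason, resting every safety statement on dosed patients would go too far.

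**Stronger readings that the documents do not support.**

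- A reader might infer that allocation-based reporting pulls every harm towards the control rate. Step 4 shows that this fails for general events if undosed patients are sicker.
- A reader might infer that per-protocol efficacy and intention-to-treat safety both lean towards FBT. The primary endpoint counts non-delivery as failure, which works against the arm in which it occurs. The only per-protocol exclusion stated is refusal of consent, in the Informed consent section; nothing says that undelivered patients are removed.
- A reader might infer that the plan itself presents limits that are too tight, or a safety test with reduced power. It plans neither. The issue with limits arises only if one is computed on the allocated number.

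**Conclusion.** The point holds for FBT-specific events. The plan's only safety denominator is the allocated one, and for a blood culture after FBT or a serious adverse event possibly related to FBT that denominator is wrong whenever any allocated patient goes undosed. The rate is then multiplied by the delivered share, and a zero-event one-sided 95% limit of 15.3% on 18 patients should be 16.2%, 17.1% or 19.3% with 17, 16 or 14 dosed. The effect is small for one undosed patient and noticeable for four. The dosed numbers are assumptions, since no non-delivery rate is given. The limits also assume that someone computes one, which is likely in a safety pilot but not specified.

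For general events such as sepsis the direction of bias is not known, and neither denominator is sufficient alone. This is an omission that is cheap to repair. It does not undermine the planned intention-to-treat comparison.

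**What to change.** In the Statistical plan, keep intention-to-treat as the randomised comparison for all safety endpoints and add text along these lines:

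*All safety endpoints will also be reported by treatment received. The number of patients given at least one FBT will be stated. For positive blood cultures after FBT and serious adverse events possibly related to FBT, that number will be the denominator, with exact 95% confidence intervals. Conclusions on general adverse events will draw on both the intention-to-treat and the treatment-received tables.*

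The cost is one sentence or two in the plan and one extra table. No new data are needed, because the FBT procedure must already be documented for each patient. The downside is that the treatment-received comparison is not randomised and may leave out sicker patients of the FBT arm. It should be labelled as such and shown beside the intention-to-treat table. No clinical procedure or stopping rule changes.

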## Hypothesis and aims:

We hypothesise that FBT will be feasible as first-line treatment of postantibiotic diarrhoea in the critically ill, incl. those with uncomplicated C. dif. infection.

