## Informed consent procedure:

[figure not shown]
All patients with capacity will be asked to provide a prospective written informed consent (See Appendix 3). For patients without capacity, a deferred consent procedure will take a place. In this case, an independent clinician will review and sign that the patient is lacking capacity and he/she fulfils all criteria to be enrolled to the

Unique Protocol ID: 2021-002290-25 22.9.2021 Protocol version 9.2

study. The patient's next of kin will be informed about the study as soon as practical with the aid of information leaflet (Appendix 3). The patient will be asked to provide and sign informed consent as soon as he/she regains the capacity to do so. In case of consent refusal, patient's data will not be used in per-protocol analysis.

22.9.2021 Protocol version 9.2

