## Control group:

- we will wait for spontaneus retreat of diarrhea, which is a standard of care.
- in the subset of patients with C. dif. positivity, the patients receive 250 mg of vancomycine every 6 hour (with rescue option of conversion to i.v. tigecycline).

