## Direct access to source data/documents:

Whole FBT procedure must be properly recorded in accordance with the rules on medical records and the documentation must be store for 10 years. The patient documentation shall include the performance indication, performance record, informed consent to FBT and information obtained during subsequent visits. The documentation must be kept to allow for an additional assessment of possible early and late side effects of the method. Furthermore, it will be recorded from what 7 donors the extract was used for each individual patient.

Donor documentation includes the results of clinical and laboratory testing, a completed and signed questionnaire confirming the absence of exclusion criteria and informed consent to the use faeces for medical purposes. For each frozen faecal extract, the date of freezing and, where appropriate, the place of preservation must be indicated in addition to the donor identification.

The examiner and the medical facility will allow for clinical trial monitoring, audits, oversight of the ethics committee, inspection authorities inspection and access to source documents.

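### Non-delivery counts as primary-endpoint failure, yet the endpoint is compared only in an undefined per-protocol set that would ordinarily drop undelivered patients

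*Combined protocol and SAP*

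**What the plan says.** The Primary end-point section gives a two-part definition: "Treatment failure is defined as either failure to administer allocated treatment for any reason or the presence of diarrhoea on day 7 after randomisation". The Abstract agrees, describing treatment failure as that "which is defined as treatment either not being delivered or effective".

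The Statistical plan reports safety by intention-to-treat and then states: "Primary outcome will be compared by as unadjusted hazard ratio of not being cured (with 95% interval) in a per protocol analysis". No other analysis of the primary outcome in the whole trial population is given.

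The per-protocol set is not defined. The only rule attached to it is in the Informed consent procedure: "In case of consent refusal, patient's data will not be used in per-protocol analysis". Nothing says whether patients who did not receive their allocated treatment stay in.

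Feasibility is the trial's purpose. The hypothesis reads: "We hypothesise that FBT will be feasible as first-line treatment of postantibiotic diarrhoea in the critically ill". The Sample study size section says: "This is a pilot trial, with primary outcome being feasibility and safety of faecal bacterial transplantation".

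**The concern.** The endpoint and its analysis set pull in opposite directions. The endpoint is built to count patients whose treatment could not be given. A per-protocol set, as the term is normally used, removes those same patients. What would then be compared is day-7 diarrhoea among patients who were treated, which is a different and more favourable quantity.

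The removal would also be uneven between arms. For C. dif.-negative controls the plan is: "we will wait for spontaneus retreat of diarrhea, which is a standard of care". Such a patient has nothing that can go undelivered. C. dif.-positive controls are allocated vancomycin and can have non-delivery, but the documents give no C. dif. mix, so the degree of imbalance is unknown. Patients would be dropped after randomisation, in an open-label trial, in a way that tends to help FBT and the non-inferiority claim.

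If instead the set was meant to be all randomised patients less consent refusals, it fits the endpoint. The plan does not say so, and the choice could then be made once allocation and outcomes are known.

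**Working it through.** **Inputs, all from Sample study size:** 36 patients randomised 1:1, so n = 18 per arm; control success 45%; FBT success 66% (27/41); margin 20 points; one-sided 5%; power 80%. The number undelivered, k of 18 FBT patients, is not in the documents. It is assumed, from 0 to 4.

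**The plan's own figure.** With unpooled variance, n per arm = [0.45×0.55 + 0.66×0.34] × (1.645 + 0.842)² / (0.21 + 0.20)² = 17.36. This rounds up to 18 per arm, 36 in total, so the stated size reproduces. Normal-approximation power at 18 per arm is 81.3%.

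**Size of the gap.** The Sample study size section does not say whether its 66% already counts undelivered patients, so there are two cases.

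- (A) 66% is success among patients actually treated. All-randomised success = 0.66 × (18 − k)/18; per-protocol success is 66% throughout.
- (B) 66% already counts non-delivery as failure. All-randomised success is 66% throughout; per-protocol success = 0.66 × 18/(18 − k).

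| k | (A) all randomised | (A) per protocol | gap, points | (B) all randomised | (B) per protocol | gap, points |
|---|---|---|---|---|---|---|
| 0 | 66.0% | 66% | 0 | 66% | 66.0% | 0 |
| 1 | 62.3% | 66% | 3.7 | 66% | 69.9% | 3.9 |
| 2 | 58.7% | 66% | 7.3 | 66% | 74.3% | 8.3 |
| 3 | 55.0% | 66% | 11.0 | 66% | 79.2% | 13.2 |
| 4 | 51.3% | 66% | 14.7 | 66% | 84.9% | 18.9 |

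**Offset from undelivered controls.** Under (A), with j undelivered controls and 45% success among treated controls, the shift in FBT minus control = 0.66k/18 − 0.45j/18. Each undelivered control takes back 0.45/18 = 2.5 points. For k = 2 the shift towards FBT is 7.3, 4.8 and 2.3 points for j = 0, 1 and 2. It favours FBT unless j exceeds about 1.5 times k (0.66/0.45 = 1.47).

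**Power on each analysis set.** Under (A), with control success 45% and j = 0, power = Φ((p − 0.45 + 0.20)/SE − 1.645). For all randomised patients, SE = √[p(1 − p)/18 + 0.45×0.55/18], with p from the table. For per protocol, p = 0.66 and the FBT denominator is 18 − k. The last column is the total needed to restore 80% with all randomised patients.

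| k | power, all randomised | power, per protocol | total for 80% |
|---|---|---|---|
| 0 | 81.3% | 81.3% | 36 |
| 1 | 73.8% | 80.3% | 44 |
| 2 | 65.4% | 79.3% | 54 |
| 3 | 56.5% | 78.1% | 70 |
| 4 | 47.6% | 76.8% | 90 |

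At the same k, moving to all randomised patients costs 6.5, 13.9, 21.6 and 29.2 points of power for k = 1 to 4. Under (B), power with all randomised patients stays at about 81%.

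**What a separate delivery estimate would show.** Exact 95% intervals for the proportion delivered in the FBT arm: 18/18, 81.5–100%; 17/18, 72.7–99.9%; 16/18, 65.3–98.6%; 15/18, 58.6–96.4%; 14/18, 52.4–93.6%.

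**The case against.** The strongest reply is that the contradiction is conditional. The only stated rule on the per-protocol set is the consent exclusion, and reading the set as all randomised patients less refusals is consistent with the endpoint. On that view the plan has an undefined term, not an analysis that removes undelivered patients. This is right as far as it goes. But the consent rule does not say it is the only exclusion, and naming the set per protocol, in contrast to intention-to-treat for safety, points towards the usual meaning.

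Second, exposure may be small. The exclusion criteria already remove patients who cannot tolerate an enema or in whom transplantation is judged not feasible, and FBT is scheduled for the day after randomisation. This stands: k could be 0, and the larger values of k have no support in the documents.

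Third, delivery could still be tabulated, since "Whole FBT procedure must be properly recorded in accordance with the rules on medical records", and screening failures on the clinician-judgement criterion (unsafe or not feasible) are to be reported separately. That captures feasibility before randomisation. No table of delivery after randomisation is planned.

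Fourth, the direction is not certain. The Sample study size section describes the population as C. dif.-positive, where controls receive vancomycin. The Abstract, the subgroup plan and the Control group section all include C. dif.-negative patients, so the asymmetry remains but its extent is unknown.

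Finally, the power figures use the risk-difference margin of the Sample study size section, not the hazard ratio of the Statistical plan. That mismatch is a separate matter.

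**Conclusion.** The concern holds. On the ordinary meaning of per protocol, the only planned whole-trial comparison of the primary endpoint cannot register one of its two components, and that component carries the feasibility question. On the alternative reading the conflict disappears, but the documents do not adopt it.

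The size depends on an unknown number undelivered. Each undelivered FBT patient moves the FBT success rate by about 4 points (3.7 under A for every patient; 3.9 under B for the first, rising thereafter). Undelivered controls reduce the shift. The direction favours FBT as long as non-delivery falls mainly on the FBT arm. The sample size of 36 is not in dispute. Because this is the primary analysis of an open-label trial, it must be settled before outcomes are seen. Confidence is medium, because the key term is undefined.

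**What to change.** In the Statistical plan:

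- Make the primary analysis all randomised patients as allocated, with non-delivery scored as failure as the Primary end-point section requires. Except only those whose data cannot be used because consent was refused. The consent section bars refusers' data from the per-protocol analysis only, so say explicitly how they are handled in this set.
- State what counts as administered in each arm, including for controls allocated to waiting and for those allocated vancomycin.
- Define the per-protocol set and keep it as a supportive analysis, which also suits the non-inferiority reading.
- Report the components separately: the proportion of the FBT arm with FBT delivered, with an exact interval, and day-7 diarrhoea by arm. This is needed even after the change, because waiting controls still cannot fail on delivery.

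The cost is a few sentences and no new data. The FBT result will look less favourable if any FBT goes undelivered, and under (A) power falls as tabulated. For a pilot it is more sensible to state the lower power than to enrol more patients.

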## Study subjects:

- Inclusion Criteria: All of the following: Informed consent (see below), Age > 18 yrs., In-patient in ICU or HDU (incl. burn unit) and expected to stay for >7 days, Diarrhoea following antibiotic treatment defined as 3 or more stools per day or Bristol type 7 stool in the volume >300 ml/day if stool derivative device is in place, persisting for 24 hours despite enteral feeding formula has been stopped.
- Exclusion criteria: Death appears imminent or ceilings of care put in place, presence of new-onset sepsis defined as per 2016 definition, lactate >2.0 mM, colon diameter > 9 cm on plain AXR, the necessity of ongoing antibiotic treatment for another reasons. Unable to tolerate enema for any reason (e.g. surgery of the GI tract in the past year). Pregnant and lactating woman. Patients with a history of severe anaphylactic food allergy, any other reason

22.9.2021 Protocol version 9.2

which — as per judgement of the treating clinician — makes faecal transplantation unsafe or not feasible (Note: All screening failures based on this criterion will be reported separately, inc. the reason why it was considered unsafe or not feasible to proceed).

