#### Procedures at baseline:

#### Day 0

In patients with diarhea, after confirmation of negative pregnancy test in fertile women informed consent will be subscribed. The drug chart will be reviewed and all medication that can be contributing to diarhea will be stopped if it is considered safe to do so. Abdominal X ray will be performed to rule out pneumoperitoneum or megacolon. After obtaining baseline stool sample (sent for study analyses but also for GDH, C. dif. toxins A and B and faecal calprotectin), blood sample will be tested for standard tests ( biochemistry, blood count, etc.). Stool and plasma samples will be frozen at -80 C for later analysis.

Randomisation will be performed by sealed envelope in the evening of day No.0. Enteral nutrition will be stopped at 18:00 at the latest.

### Day 1

The patient will be physically examined in the morning, including the determination of the degree of SOFA score (a set of laboratory results and examinations estimating organ function). Stool and plasma samples will be frozen at -80 C for later analysis. The frequency, amount and structure of the patient's stools will be recorded. Patients will be treated for their primary disease throughout the study according to established standard procedures.

In both groups adequate hydratation will be taken care of by replacing the fluids lost by diarrhea with infusion. Throughout the treatment, we monitor the patient's vital functions (body temperature, heart rate, blood pressure, blood oxygen saturation)

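### The day-7 comparison should be a risk difference matching the sample-size calculation, with one prespecified adjustment for pre-randomisation stool output: a modest gain, not the correction of a bias

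*Combined protocol and SAP*

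**What the plan says.** The Statistical plan gives the primary analysis in one sentence: "Primary outcome will be compared by as unadjusted hazard ratio of not being cured", with a 95% interval, in a per protocol analysis. It names no covariate. The only other comparison described there is a separate analysis of C. dif positive patients.

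The Primary end-point section makes the outcome binary: on day 7 a patient has failed or has not. Failure means either that the allocated treatment was not given or that diarrhoea is present.

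The Sample study size section works on a different scale: "We plan to randomise 36 patients in 1:1 ratio", and "36 patients are required to be 80% sure that the upper limit of a one-sided 95% confidence interval" will rule out a 20-point disadvantage on the difference in proportions. It equates this to a two-sided 90% interval.

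Stool output appears in three places before or near the start of treatment:
- Study subjects sets the entry threshold, "3 or more stools per day or Bristol type 7 stool in the volume >300 ml/day" (the volume applying where a collection device is in place). Assessment of primary outcome uses the same threshold on day 7.
- Procedures at baseline, under Day 1, has "The frequency, amount and structure" of stools recorded. Randomisation is on the evening of day 0, by sealed envelope, with no stratification described.
- Monitoring of safety says that the frequency, volume and character "of stools will be recorded in 12 hour intervals", without saying when this begins.

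The table of study procedures has no row for stool output.

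**The concern.** Two things in the same sentence deserve attention. A hazard ratio describes time to an event, but the endpoint is a status on one day and the 20-point margin is on the risk-difference scale. A reader could not set the planned result directly against the margin that justified 36 patients.

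Second, the diarrhoea part of the endpoint is the follow-up value of a quantity that must be known at entry. Some association between the two is plausible. With 18 per arm and no stratification described, the arms may differ visibly in initial severity. If no adjusted analysis is named in advance, any adjustment made after seeing such a difference is post hoc and open to challenge.

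**Working it through.** **Inputs.** From Sample study size: 36 patients, 1:1, so 18 per arm; control success 45% ("as compared to 45% cured by oral metronidazole"); FBT success 66%; margin 20 points; one-sided 5%; power 80%. In failure terms this is 55% v 34%. The prognostic strength of entry output is not in the documents. It is assumed here as an odds ratio (OR) for failure of 1.5, 2 or 3 per SD.

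**1. The plan's own figure.**
Variance sum = 0.45×0.55 + 0.66×0.34 = 0.2475 + 0.2244 = 0.4719.
n per arm = (1.645 + 0.842)² × 0.4719 / (0.21 + 0.20)² = 6.18 × 0.4719 / 0.1681 = 17.4, rounded up to 18, so 36 in total. The stated figure reproduces, on the risk-difference scale. Power at 18 per arm by this formula is 81%.

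**2. Chance imbalance.** The SD of the between-arm difference in a standardised covariate is √(2/18) = 0.333. P(imbalance of 0.5 SD or more, either direction) = 2 × [1 − Φ(0.5/0.333)] = 2 × [1 − Φ(1.5)] = 0.134. For one given direction it is about 0.067.

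**3. Effect on the unadjusted difference.** A rough approximation is 0.5 × ln(OR) × mean p(1−p), where the mean is 0.4719/2 = 0.236:
- OR 1.5: 0.5 × 0.405 × 0.236 = 4.8 points
- OR 2: 0.5 × 0.693 × 0.236 = 8.2 points
- OR 3: 0.5 × 1.099 × 0.236 = 13.0 points

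This overstates the larger effects, because averaging over the covariate flattens the relation. Simulation (20,000 trials, 18 per arm, 55% v 34% failure) gives about 4 to 5, 7 to 8 and 10 to 11 points.

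**4. Precision and power, averaged over all randomisations.** The simulation compares the unadjusted risk difference with a linear model containing one covariate. Power is for ruling out the 20-point margin with the one-sided 95% limit.

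| OR per SD | SD of difference, unadjusted v adjusted | Power, unadjusted | Power, adjusted, ordinary robust SE | Power, adjusted, HC3 SE with t reference |
|---|---|---|---|---|
| 1.5 | 0.163 v 0.164 | 79–80% | 79% | 76–77% |
| 2 | 0.161 v 0.157 | 79–80% | 81–82% | 79% |
| 3 | 0.162 v 0.149 | 79–80% | 85–86% | 83% |

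The variance ratio at OR 2 is (0.157/0.161)² = 0.95 and at OR 3 is (0.149/0.162)² = 0.85, so the reduction is about 0%, 5% and 15% across the three rows. With no prognostic effect, adjusted power is 78% (ordinary robust SE) or 76% (HC3).

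**5. Validity of the unadjusted analysis.** Across simulated scenarios its mean was 0.21 for a true 0.21. Its error rate at the margin was 0.048 to 0.058 against a nominal 0.05.

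**6. Accuracy when the arms do differ.** Take imbalance beyond 0.4 SD in one direction (probability 1 − Φ(0.4/0.333) = 1 − Φ(1.2) = 0.115). If the FBT arm is the more severe, unadjusted power at the design rates falls to 69%, 62% or 51% (OR 1.5, 2, 3), against 74%, 76% or 80% adjusted. If the FBT arm is the milder and the truth lies at the margin, false non-inferiority is 9%, 13% or 16% unadjusted, against 3–4% adjusted.

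**The case against.** The strongest reply is that nothing here is an error. Randomisation makes the unadjusted comparison valid, and its interval already allows for chance imbalance. This stands. A reader might infer from the shifts in step 3 that the planned result is biased or its error rate inflated. Step 5 shows neither.

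A reader might also infer that a usable baseline covariate is already on file. The documents do not go that far. Study subjects requires the threshold to be met but does not require the value to be kept as data. The Day 1 record follows randomisation and is not stated to precede FBT. Only the intervention arm may receive loperamide before FBT, or a saline enema if C. dif positive, so output after randomisation could depend on allocation.

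Further points that stand:
- No passage says that entry output predicts day-7 failure. The ORs are assumptions.
- Failures through non-delivery need not depend on stool output. The simulation ties the whole endpoint to it, so many such failures would shrink the gain.
- Nothing in the documents makes multiples of the count and volume thresholds equivalent. A mixed-scale measure may predict less well than the single normal covariate simulated.
- C. dif status is a rival covariate, since it determines treatment in both arms. About 18×0.55 + 18×0.34 = 16 failures are expected, so only one covariate is realistic. C. dif positive patients already have a separate analysis.
- The power figures describe a risk difference with 18 analysed per arm. They do not describe the planned hazard ratio, and a per protocol set may be smaller.

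These points limit the claim but do not remove it. Entry output must be known before randomisation, one covariate is affordable, and the unadjusted result would remain on view.

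**Conclusion.** The point holds as an inexpensive improvement. The clearest part needs no assumption about prognosis: the planned hazard ratio fits neither a yes/no day-7 outcome nor the risk-difference margin behind the 36 patients, and the 95% interval attached to it differs from the two-sided 90% interval used in the design.

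The adjustment is worth less. On average it adds about 0 to 6 points of power for an OR per SD of 1.5 to 3, and can cost a few points with a conservative standard error and a weak covariate. Its better justification is the 13% chance of a 0.5 SD imbalance, which would move the difference by about 4 to 11 points against a margin of 20, with no prespecified analysis to address it. All these sizes rest on the assumed prognostic strength, a single well-behaved covariate and 18 analysed per arm.

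**What to change.** In the Statistical plan:
1. Replace the hazard ratio with the difference in day-7 failure proportions and its two-sided 90% interval, to be read against the 20-point margin in Sample study size.
2. Prespecify one adjusted risk difference, as the primary or a named sensitivity analysis, with the unadjusted difference beside it. Use a linear model with robust standard errors, or logistic regression with standardisation, and name the standard error in advance.
3. Restrict the covariate to stool output in the eligibility window before randomisation. State that the Day 1 record is not used.
4. Fix the rule for the two scales in advance, for example output as a multiple of the protocol threshold (count/3 or volume/300 ml) plus an indicator for device use.
5. Add the eligibility count or volume to the case report form and to the procedures table.

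Cost: analysis-plan wording, one data item and a scaling rule that is a judgement. The gain is nil or slightly negative if entry output is weakly prognostic or many failures are non-delivery. The change should be made before any unblinded analysis.
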